Effectiveness will be evaluated as the absence of pregnancy during VeraCept use for up to12 months. Pregnancies judged to have occurred during study device use (determined by ultrasound and medical assessments), for which the estimated date of conception was within 7 days after study device removal or calculated date of expulsion, will be included in the per protocol analysis of pregnancies.

The Pearl Index (and 95% confidence intervals) will be calculated through 12 months for cycles in subjects aged 18-35 at the time of study device placement, excluding the following cycles (unless the subject became pregnant in the cycle):

- When back-up contraceptive or emergency contraceptive use was documented on the daily diary
- When the subject denied having any intercourse.

All pregnancies will be counted in the intent to treat analysis.

Life table analyses will be used as further assessment of pregnancies. Secondarily the Pearl index and life table analyses will be done through 3 years.

Safety and Other Outcome Measures

VeraCept ease of placement, removal and placement success will be descriptively summarized.

Safety evaluations will be based on the incidence of adverse events and serious adverse events changes from baseline in other assessments (examinations and vital signs) and by relationship to the study device or study device placement procedure. Study device tolerability will be based on changes in bleeding and spotting patterns and study discontinuation (including reasons for discontinuation).

Safety analyses will be based on the experience of all subjects who had attempted study device placement and provided any relevant data. Tolerability analyses will be based on the experience of all subjects who received a study device and provided any relevant data.

Subjects will record frequency and intensity of vaginal bleeding through a daily diary. The number of bleeding or spotting days will be summarized for each cycle. In addition, bleeding and spotting will each be summarized separately. Bleeding analyses will include all subjects who had a study device placed and have at least 1 cycle where they were not pregnant and were providing bleeding-related diary data on the days in the reference period.

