In general, summaries of quantitative variables will include the sample size, mean, median, standard deviation, minimum, and maximum. For qualitative (categorical) variables the summaries will include the number and percentage of subjects in each category.

SAMPLE SIZE

No formal sample size calculations were performed for the study. It is estimated that with 225 subjects enrolled with age 18-35, a 12-month Pearl Index of 0.6 (1 observed pregnancy), and 2,015 evaluable cycles, we will observe a 95% confidence interval for the 12 month Pearl Index of (0.1, 3.3).

2.015 evaluable cycles assumes that in the overall study:

- Each subject will average10 evaluable cycles of VeraCept use
- 1% of subjects will not provide any diary data and will be excluded from the primary efficacy population
- Subjects will not have intercourse or will use backup contraception in 9.2% of cycles

ABBREVIATIONS AND DEFINITIONS OF TERMS

AE	Adverse Event
BMI	Body Mass Index
BP	Blood Pressure
BUN	Blood Urea Nitrogen
BV	Bacterial Vaginosis
C	Celsius
CBC	Complete Blood Count
CCTN	Contraceptive Clinical Trials Network
CFR	Code of Federal Regulations
cm	Centimeters
CRF	Case report forms
Cu	Copper
CVR	Contraceptive vaginal ring
d	Day
DHHS	Department of Health and Human Services
dL	Deciliter Deciliter
DSMB	Data Safety Monitoring Board
EC	Emergency contraception
eCRF	Electronic case report form
EDC	Electronic data capture
ECYC	Evaluable for Cycle Control
EE	Efficacy Evaluable
EMR	Electronic medical records
ENDTX	End of treatment
EP	Evaluable for Pregnancy
F	Fahrenheit
FDA	Food and Drug Administration
FSH	Follicle Stimulating Hormone
	Gram
GCP	Good Clinical Practices
GnRH	Gonadotropin-Releasing Hormone
hCG	Human Chorionic Gonadotropin
HD	Health Decisions
HPV	Human Papillomavirus
ICH	International Conference on Harmonization
IEC	Independent Ethics Committee
IND	Investigational New Drug
IRB	Institutional Review Board
ITT	Intent-To-Treat
IUD	Intrauterine Device
kg	Kilograms
L	Liter
LTFU	Lost to follow up
MedDRA	Medical dictionary for regulatory activities
MITT	Modified Intent To Treat
mg	Milligrams
mL	Milliliter
11115	Minimo

mm	Millimeter
NDA	New Drug Application
NIH	National Institutes of Health
N/A	Not Applicable
OC	Oral Contraceptive(s)
Pap Test	Papanicolaou Test
PD	Pharmacodynamics
PK	Pharmacokinetics
PP	Per-protocol
SAE	Serious Adverse Event
SAP	Statistical Analysis Plan
SAS	Statistical Analysis Software
SCCC	Statistical and Clinical Coordinating Center
SCRN	Screening

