12.3.1 Monthly Phone Contact (up to 52 Weeks)

Subjects will be contacted by phone each month, after her menses, to confirm completion of the monthly diary for:

- The need for additional contraception;
- Use of concomitant contraception;
- Use of concomitant medications;
- Documentation of menstrual and intermenstrual bleeding;
- Assess if there have been any adverse events since the last contact; and
- Resolution of any prior serious adverse events or adverse events.

12.4 Long-term Follow-up post 52-week visit (Every 6 Months: Months 18-30 (±4wks) and 3 yrs (-3wks/+4wks) /Exit visit

The subject will return for follow up after their Week 52 visit, every 6 months, if they choose to continue with the study visit. During these visits, the subject will be evaluated for:

- Vital signs and weight
- General physical exam (same as at Screening Visit)
- Pelvic exam (string check)
- Transvaginal ultrasound to document VeraCept position (only if indicated)
- Pregnancy test, urine
- Interval and concurrent medications
- Adverse events
- Verify sexual activity

Document any back-up contraception methods

Additionally, at the final visit at 3 Years / Exit visit, the following will also be performed:

- Transvaginal ultrasound to document VeraCept position
- VeraCept Removal
- Urine pregnancy test will be done 17 days after removal/study exit by the subject at home, with a follow up call by the study coordinator or PI required to document results.

A 2-week supply of hormonal contraceptive pills will be provided to the subject by the site as a contraceptive option for the first two weeks after VeraCept removal.

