20.6 Primary Outcome

The primary outcome measure is effectiveness and will be evaluated as absence of pregnancy during VeraCept use for up to 12 months. Pregnancies judged to have occurred while a study device was in place (determined by ultrasound and medical assessments) will be included in the analysis of pregnancies.

For the primary evaluation of effectiveness, the Pearl index (and 95% confidence intervals) will be calculated through 12 months for cycles in subjects aged 18-35 at the time of VeraCept placement, excluding the following (unless the subject became pregnant in the cycle):

- Cycles where back-up contraception use was documented on the daily diary
- Cycles with no intercourse.
- Cycles in which emergency contraception was used

The EP population will be used for the primary evaluation of effectiveness.

Life table analyses will be used as further assessment of pregnancies. Secondarily the Pearl index and life table analyses will be done through 3 years.

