## 3.7 Efficacy Analyses

## 3.7.1 Efficacy Analyses for Year 1 Data

Primary efficacy analysis was performed for the first year of the study (through Day 364) for Evaluable for Pregnancy population, by using Pearl Index. Pearl Index is defined as the number of pregnancies in 100 woman-years of method use. Pearl Index was calculated in subjects aged 18-35 at the time of VeraCept placement through the date of VeraCept removal or pregnancy, excluding the following cycles, unless the subject became pregnant in that cycle:

- When back-up contraception use was documented on the daily diary
- When the subject had no intercourse.

The Pearl Index formula is:

$$r = \frac{n}{L} \times 1300 = \frac{\text{Number of pregnancies}}{\text{Number of woman-cycles of pregnancy-risk}} \times 1300$$

where n is the number of pregnancies, and L is the number of woman-cycles, i.e., sum of the number of cycles each woman used the VeraCept up to and including the cycle of conception or until the time of VeraCept removal/expulsion, whichever comes earlier. The cycles of pregnancy-risk will be calculated as (Date of VeraCept removal/expulsion – Date of VeraCept placement + 1) / 28 for women who are not pregnant, and as (Date of pregnancy – Date of VeraCept placement + 1) / 28 for women who became pregnant

during the study. On-treatment pregnancies are defined to be pregnancies for which the estimated date of conception was within 7 days after study device expulsion or removal (the earlier of expulsion and removal dates will be used). The last cycle of pregnancy-risk can be a partial cycle and the partial cycle at risk is determined by dividing the number of days at risk in the cycle by 28 (e.g., 14/28 = 0.5 cycle of risk). If a cycle has a day with no information about backup contraception, that cycle will be excluded from the analysis (unless the subject became pregnant in that cycle).

To get the confidence interval (CI) for the Pearl Index, first the CI for the n (number of pregnancies) will be approximated by Poisson distribution sample mean's CI as

$$(\frac{\chi^{2}(\alpha/2;2n)}{2},\frac{\chi^{2}(1-\alpha/2;2n+2)}{2})$$

where  $\chi^2(\alpha/2;2n)$  in the lower limit is the Chi-square distribution (degrees of freedom = 2n) percentile with lower tail area (probability)  $\alpha/2$ , and  $\chi^2(1-\alpha/2;2n+2)$  in the upper limit is similarly defined. If n = 0, the lower limit will be set as 0.

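### The SAP drops a whole Year 1 cycle for one day without backup-contraception information, an exclusion the protocol lacks, and plans no Year 1 result without it

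*SAP*

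**What the plan says.** Protocol 20.6 calculates the primary Pearl Index "excluding the following (unless the subject became pregnant in the cycle"). It lists three kinds of cycle: "Cycles where back-up contraception use was documented on the daily diary", cycles with no intercourse, and "Cycles in which emergency contraception was used". The protocol's Investigational Plan Summary words the intercourse item as an active statement by the woman: "When the subject denied having any intercourse". Neither place makes missing information a ground for exclusion.

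SAP 3.7.1 lists backup use and no intercourse, then adds: "If a cycle has a day with no information about backup contraception, that cycle will be excluded from the analysis". The same exception follows, "unless the subject became pregnant in that cycle". The section gives no reason for the addition.

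The SAP treats missing records differently elsewhere. Sections 3.8.4 and 3.8.5 impute missing discomfort and bleeding days when a cycle has at least 14 days of data. Section 3.7.2 estimates exposure for Year 2 and Year 3 cycles with no contact data, and also runs the analysis without those cycles (Tables 14.2.1-Y2, -Y2M, -Y3 and -Y3M). Year 1, which SAP 3.1.2 calls the main analysis, has the single Pearl Index Table 14.2.1-Y1.

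**The concern.** A missing entry is not documented backup use, so this is a new exclusion in the primary analysis. If cycles with a blank were dropped whatever their outcome, and blanks were unrelated to conception, the cost would be precision only. Here pregnancy-free cycles leave the denominator L and pregnancies stay in the numerator n. The main estimate then depends partly on how completely diaries were filled in, and the plan gives the reader no way to see by how much.

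The effect also goes beyond Year 1. SAP 3.7.2 adds the Year 1 pregnancy-risk cycles to the 2- and 3-year denominators. Its Step B uses each woman's share of Year 1 diary cycles that were at risk to estimate later missing cycles. If cycles lost to a blank day count there as not at risk, the estimated later exposure shrinks too.

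**Working it through.** **Inputs from the documents.** The sample size text of the protocol summary and SAP 2.5 give 225 subjects aged 18–35, one pregnancy, 2,015 evaluable cycles and a Pearl Index of 0.6. The protocol text adds an average of 10 evaluable cycles per subject, 1% of subjects with no diary data, and "Subjects will not have intercourse or will use backup contraception in 9.2% of cycles". SAP 2.4.1 sets the cycle at 28 days. SAP 3.7.1 gives the Pearl Index as 1300 × n/L, with chi-square (exact Poisson) limits.

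**Input not in the documents.** The share p of days without backup information is nowhere given. The values below are assumptions.

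**Reproducing the plan's figures.** 225 × 10 × 0.99 × 0.908 = 2,022.6. Rounding 222.75 subjects down to 222 gives 222 × 10 × 0.908 = 2,015.8, in line with 2,015. The Pearl Index is 1300 × 1/2,015 = 0.645, stated as 0.6. The SAP formula at L = 2,015 gives limits of 0.02 and 5.5716 × 1300/2,015 = 3.59. The documents state (0.1, 3.3), which is a separate discrepancy; the SAP formula is used here throughout.

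**Effect of the rule.** If blanks fall independently across days, a cycle survives with probability s = (1 − p)^28. Then L = 2,015 × s with n unchanged, so the Pearl Index and both limits are multiplied by 1/s.

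| Assumed blank days p | Cycles lost | L | Pearl Index, n = 1 | Upper limit, n = 1 |
|---|---|---|---|---|
| 0 | 0% | 2,015 | 0.65 | 3.59 |
| 0.1% | 2.8% | 1,959 | 0.66 | 3.70 |
| 0.5% | 13.1% | 1,751 | 0.74 | 4.14 |
| 1% | 24.5% | 1,521 | 0.85 | 4.76 |
| 2% | 43.2% | 1,144 | 1.14 | 6.33 |

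At p = 1%, 2,015 − 1,521 = 494 cycles go. With n = 0 the Pearl Index stays at 0, and the upper limit at p = 1% rises from 2.38 to 3.15.

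**Sensitivity to clustering.** If the same 1% of blank days filled whole cycles, only 1% of cycles would be lost. L would be 2,015 × 0.99 = 1,995 and the Pearl Index 1300/1,995 = 0.65. If no cycle had more than one blank, the loss would be 28 × 1% = 28%. Independence therefore lies near the upper end of what a given p can do.

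**The definition of L.** SAP 3.7.1 also gives cycles at risk as calendar days from placement to removal, expulsion or pregnancy, divided by 28. Read alone, that formula deletes no cycle. The section needs to say how it combines with the exclusions.

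**The case against.** The strongest case for the SAP is that a cycle should count as exposure only when it is known to be at risk. The protocol's Evaluable for Pregnancy definition (20.1) asks for a diary cycle with intercourse and without backup, which an unknown day cannot establish. Counting unknown cycles as at risk could understate failure, and protocol section 20 leaves detail to the SAP. As a conservative choice the rule is defensible, and that stands. It does not explain why Year 1 alone lacks a result with and without the rule.

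Several stronger readings are tempting, but the documents do not support them.

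- *The SAP introduced the asymmetry between pregnancies and exposure.* It did not; the protocol keeps pregnancies from excluded cycles. Only the missing-day trigger is new.
- *The rule flatters the device.* It works in the opposite direction.
- *Most blank days could be filled from the monthly calls.* Protocol 12.3.1 lists "Use of concomitant contraception" among the items, but as a check that the diary is complete. The questions that SAP 3.8.9 summarizes are need for additional contraception, intercourse and its frequency, over 30-day months and not 28-day cycles. How many blanks the calls could resolve is unknown. On the other side, these calls and the diary review at visits (protocol 12.3) may have kept blanks few.
- *The trial will miss 2,015 cycles because this loss was not budgeted.* The plan does not say what its average of 10 evaluable cycles out of 13 already absorbs. If 15% discontinued evenly over the year (the top of the range in protocol section 1; the even spread is an assumption), mean use would be 13 × (1 − 0.15/2) = 12.0 cycles. That leaves 1 − 10/12.0 = 17% unexplained, which could include diary loss. No formal sample size calculation or success threshold rests on 2,015.
- *The protocol's rule should now replace the primary denominator.* SAP 3.1.2 and 3.7.1 report the Year 1 analysis as already performed. A switch after that would be a post hoc change that can only lower the Pearl Index or its upper limit.

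**Conclusion.** The point holds as a departure from the protocol that needs to be made visible. SAP 3.7.1 adds a missing-day exclusion that protocol 20.6 does not contain. Measured against the protocol's rule, it raises the Pearl Index and both limits by 1/(share of cycles kept) when n ≥ 1, and raises only the upper limit when n = 0. The direction is certain; the size is not. Under independent blanks and one pregnancy, the effect runs from negligible (0.65 to 0.66 at 0.1% blank days) to material (0.65 to 1.14 at 2%), and clustering reduces it. It does not show that the Year 1 result is wrong or that planned exposure was missed. The SAP was built on a Version 1.00 for Year 1 that is not among the documents, so when the rule was set cannot be seen.

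**What to change.** Leave the completed Year 1 analysis as it is. Add to the SAP:

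1. A clearly labelled sensitivity Pearl Index and life table for Year 1 using the protocol 20.6 exclusions only (documented backup use, emergency contraception, no intercourse).
2. The same Year 1 count carried into the Year 2 and Year 3 denominators, with a statement of how cycles with a missing day are treated in Step B of SAP 3.7.2.
3. The number of cycles, and of women, removed solely by the missing-day rule.
4. Use of existing phone-contact and visit records to resolve missing days where they allow it, with the number resolved.
5. One sentence reconciling the calendar-days formula for L with the cycle exclusions.

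The cost is a short SAP addition and extra runs on data already collected. The downside is that some cycles with unrecorded backup use may be counted as at risk in the sensitivity analysis, which would pull its Pearl Index down. The two results should therefore be read as a range, with neither presented as a correction of the other.

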## 3.7.2 Efficacy Analyses for the Whole Study

Post-Year 1 sexual activity and contraceptive use information can be found in the Cycle Contact CRF, which was added since the Extension study (Year 2) started, i.e., this CRF wasn't present from the beginning of the study, but added as a mid-study change. Each record in this form is for one cycle and has the following 2 key questions for determining if a cycle is pregnancy-risk or not:

- Did the subject have intercourse at least once during the cycle? (Yes, No)
- Did the subject use backup contraception during the cycle? (Yes, No)

If the answer is "Yes" to the first question and "No" to the second question, or the subject was pregnant within a cycle (determined form the Pregnancy Test form), that cycle will be considered as a pregnancy-risk cycle; otherwise, the cycle will not be considered as a pregnancy-risk cycle.

For cycles without any Cycle Contact information, e.g., neither of the above 2 "Yes"/"No" questions were answered and a subject wasn't pregnant within the cycle either, the following procedure will be used to do the estimate for the subject:

- A. find the total number of such type of cycles for that subject
- B. find proportion of pregnancy-risk cycles from Year 1 diary data of the subject, which will be calculated as the number of pregnancy-risk cycles divided by the total number of cycles from Diary CRF
- C. The number from Step A is multiplied by the number from Step B, and then rounded to 1 decimal place, which will be the estimated number of pregnancy-risk cycles where Cycle Contact information is missing for the subject.

The number from Step C will be added to the number of pregnancy-risk cycles from those without missing Cycle Contact information, and then added to the Year 1 pregnancy-risk cycles from Diary CRF data to get denominator value of the Pearl Index for Year 2 (data cut off at 26 cycles) and Year 3 (data cut off at 39 cycles). The numerator will be the number of on-treatment pregnancies by the end of Cycle 26 and Cycle 39, respectively.

The Year 2 and Year 3 analyses will also be performed without inclusion of cycles with missing Cycle Contact information, i.e., not doing estimates of pregnancy-risk through the above Steps A, B, and C.

The 95% Confidence Intervals for the Pearl Index will be calculated, by using the formula in the above Section 3.7.1, at the following 3 scenarios:

- All EP subjects
- EP subjects with at least one live birth
- EP subjects never had live birth

Life-Table (Kaplan-Meier) method will also be used to present probabilities of pregnancy-free through Year 1 (Day 365), Year 2 (Day 730), and Year 3 (Day 1095 + 2 weeks, or Study Day 1109). If a subject doesn't have an on-treatment pregnancy, the event time will be censored at that day (of study device removal, or day of last contact).

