14.1.10.4	List of Medications Used by Subjects who Failed the Insertion Procedure	ITT
14.2.1-Y1	1-Year Pearl Index	EP
14.2.1-Y2	2-Year Pearl Index - No Missing Cycle Contact	EP
14.2.1-Y2M	2-Year Pearl Index – with Estimation for Missing Cycle Contact	EP
14.2.1-Y3	3-Year Pearl Index – No Missing Cycle Contact	EP
14.2.1-Y3M	3-Year Pearl Index – with Estimation for Missing Cycle Contact	EP
14.3.0	Treatment Exposure	Safety
14.3.0T	Treatment Exposure	ITT
14.3.1.1	Overall Number and Percentage of Subjects with Adverse Events	Safety
14.3.1.1T	Overall Number and Percentage of Subjects with Adverse Events	ITT
14.3.1.2	Overall Number of Adverse Events by Severity and Relatedness to the Study Product	Safety
14.3.1.2T	Overall Number of Adverse Events by Severity and Relatedness to the Study Product	ITT
14.3.1.3C	Summary of Adverse Events by System Organ Class in Descending Order of Frequencies	Safety
14.3.1.3P	Summary of Adverse Events by Preferred Term in Descending Order of Frequencies	Safety

14.3.1.3P-Y1	Summary of Year 1 Adverse Events by Preferred	Safety
	Term in Descending Order of Frequencies	
14.3.1.3P-Y2	Summary of Year 2 Adverse Events by Preferred Term in Descending Order of Frequencies	Safety
14.3.1.3P-Y3	Summary of Year 3 Adverse Events by Preferred Term in Descending Order of Frequencies	Safety
14.3.1.4	Summary of Adverse Events by System Organ Class and Preferred Term	Safety
14.3.1.4T	Summary of Adverse Events by System Organ Class and Preferred Term	ITT
14.3.1.5	Summary of Serious Adverse Events by System Organ Class and Preferred Term	Safety
14.3.1.6	Summary of Adverse Events that Led to Premature Study Discontinuation	Safety
14.3.1.7C	Summary of Adverse Events by System Organ Class and by Severity	Safety
14.3.1.7	Summary of Adverse Events by System Organ Class and Preferred Term and by Severity	Safety
14.3.1.8C	Summary of Adverse Events by System Organ Class and by Relatedness to the Study Product	Safety
14.3.1.8	Summary of Adverse Events by System Organ Class and Preferred Term and by Relatedness to the Study Product	Safety
14.3.1.9A	Summary of Allergy-Related Symptoms by Onset Time	Safety
14.3.1.9B	Summary of Dyspareunia by Onset Time	Safety
14.3.2.1	List of Serious Adverse Events	Safety
14.3.2.2	List of Adverse Events that Led to Premature Study Discontinuation	Safety
14.3.5	Device Placement and Subject Pain During the Procedure	Safety
14.3.6	Device Expulsion or Removal and Subject Pain During the Procedure	Safety

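### In the Year 2 and Year 3 Pearl Index tables with estimation, two half-answered Cycle Contact patterns that point towards risk get no exposure, while a blank record is credited

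*SAP*

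**What the plan says.** After Year 1, exposure comes from the Cycle Contact form, which has one record per cycle and two Yes/No items: intercourse and backup contraception (SAP 3.7.2). A cycle is at risk if intercourse is Yes and backup is No, or if the woman was pregnant in it; "otherwise, the cycle will not be considered as a pregnancy-risk cycle".

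A separate route covers absent data. It opens with "For cycles without any Cycle Contact information, e.g., neither of the above 2" items being answered, and applies only if the woman was not pregnant in the cycle. Step A counts such cycles for the woman. Step B takes her Year 1 risk proportion, "which will be calculated as the number of pregnancy-risk cycles divided by the total number of cycles from Diary CRF". Step C combines them: "The number from Step A is multiplied by the number from Step B, and then rounded to 1 decimal place".

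The result is added to her other extension risk cycles and to her Year 1 risk cycles, so the denominators at 26 and 39 cycles are cumulative. A parallel version drops the estimation: "The Year 2 and Year 3 analyses will also be performed without inclusion of cycles with missing Cycle Contact information". SAP 5.2 lists both versions for each year; the estimated one for Year 2 is "2-Year Pearl Index – with Estimation for Missing Cycle Contact" (14.2.1-Y2M), with 14.2.1-Y3M for Year 3.

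For the Year 1 diary, SAP 3.7.1 has its own rule: "If a cycle has a day with no information about backup contraception, that cycle will be excluded from the analysis", unless the woman became pregnant in that cycle.

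**The concern.** No sentence deals with a record on which one item is answered and the other is blank. Such a record is not without any information, so it misses Steps A to C. Nor is it a Yes/No pair, so it lands in the default branch and counts 0.

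For two of the four half-answered patterns this puts exposure in the wrong order. If intercourse is Yes and backup is blank, or backup is No and intercourse is blank, the one known answer makes risk more likely than if nothing were known. The rule nevertheless gives that cycle less exposure than a blank one.

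A pregnancy in such a cycle still counts, so only event-free exposure is lost and the index can only move upwards. At stake are the accuracy of two secondary tables and the consistency of their missing-data rule.

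**Working it through.** **Inputs**

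- Classification rule and Steps A to C: SAP 3.7.2.
- Stand-in for Step B: the protocol's sample size section assumes 9.2% of cycles without intercourse or with backup, so B = 1 − 0.092 = 0.908. This is a planning figure, not an observed Step B.
- Year 1 exposure of 2,015 cycles and 1 pregnancy: protocol sample size section and SAP 2.5.
- Assumed, because the documents do not say: 100 to 150 women continuing, 13 cycles each in Year 2, and 1% to 5% of extension records half-answered, all of the two affected patterns.

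The plan states no Year 2 or Year 3 exposure or index to reproduce. At the Year 1 planning values the SAP formula gives 1 / 2,015 × 1300 = 0.645, in line with the stated 0.6.

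**Step 1. Apply the rule to every answer pattern (woman not pregnant)**

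| Intercourse | Backup | Exposure under the SAP | Comment |
|---|---|---|---|
| Yes | No | 1 | at risk |
| Yes | Yes | 0 | protected |
| No | No or Yes | 0 | no intercourse |
| No | blank | 0 | correct: known answer rules risk out |
| blank | Yes | 0 | correct: known answer rules risk out |
| Yes | blank | 0 | undetermined, leans to risk |
| blank | No | 0 | undetermined, leans to risk |
| blank | blank | 0.908 | Steps A to C |

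**Step 2. What the two undetermined patterns should be worth**

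If answers are missing at random, P(risk | intercourse Yes) = P(risk) / P(intercourse Yes). The divisor is at most 1, so the result is at least P(risk) = 0.908, and it cannot exceed 1. The same argument applies to P(risk | no backup). Both patterns are worth between 0.908 and 1; the SAP gives 0.

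For one woman with 13 such cycles: all blank gives 13 × 0.908 = 11.8 risk cycles; all Yes/blank gives 0.

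**Step 3. Effect on the two-year table with estimation**

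For S women and a half-answered share f:

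- as written: L = 2,015 + (1 − f) × 13S × 0.908
- corrected: L = 2,015 + 13S × 0.908

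The index is 1300 / L for one pregnancy. Its upper limit by the SAP's Poisson formula is 5.572 / L × 1300.

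| S | f | L as written | L corrected | Rise in L | Index | Upper limit |
|---|---|---|---|---|---|---|
| 100 | 1% | 3,183.6 | 3,195.4 | 0.37% | 0.408 to 0.407 | 2.275 to 2.267 |
| 100 | 5% | 3,136.4 | 3,195.4 | 1.88% | 0.414 to 0.407 | 2.309 to 2.267 |
| 150 | 1% | 3,767.9 | 3,785.6 | 0.47% | 0.345 to 0.343 | 1.922 to 1.913 |
| 150 | 5% | 3,697.1 | 3,785.6 | 2.39% | 0.352 to 0.343 | 1.959 to 1.913 |

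**Step 4. Three-year table**

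If the same women all complete Year 3, 13S becomes 26S. At 5%, L goes from 4,257.8 to 4,375.8 (S = 100, a rise of 2.8%) or from 5,379.1 to 5,556.2 (S = 150, a rise of 3.3%). At 1% the rise is 0.5% to 0.6%.

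**Step 5. Tables without estimation**

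Blank cycles add 0 there, and so do half-answered ones. Nothing is out of order and no number changes.

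**The case against.** The strongest reply is that the gap may be empty. The two items are collected in a single contact, and Protocol 19.3 has all eCRFs reviewed for completeness with queries resolved at the sites. Half-answered records could be very rare. That stands: the 1% to 5% share is an assumption. Against it, contacts may be by phone, e-mail or text message (Protocol 12.4.1, SAP 2.3), and neither document says the form forces both answers.

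A second reply is that giving no exposure when backup is unknown matches the Year 1 rule in SAP 3.7.1. It does, but the estimation tables already depart from that rule by crediting cycles with no backup information at all. The Year 1 rule therefore cannot justify zeroing the partly informative cycle while crediting the blank one. It is fair to add that Steps A to C have an evident purpose, since the form was introduced mid-study and whole records may be absent.

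Third, Step B may fall below 0.908, because a Year 1 cycle excluded for a missing backup day is not a risk cycle but can still sit in Step B's denominator. That also stands. A lower B shrinks the effect, and a woman whose B is 0 shows no inversion.

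Fourth, the example wording before Steps A to C might be read loosely enough to admit a half-answered record. The natural reading is a fully blank one, and room for two readings is itself a reason to add a rule.

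A reader might infer more than the documents support:

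- **That every half-answered record is mishandled.** Zero is right for intercourse No with backup blank, and for backup Yes with intercourse blank.
- **That the reported index is 1% to 5% too high.** That would describe an extension-only index, and none is planned. The tables include Year 1, which dilutes the effect.
- **That the rule flatters the device.** Less exposure raises the index and its upper limit. Counting a pregnancy in an otherwise excluded cycle is the plan's convention throughout, not a feature of this gap.

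**Conclusion.** The point holds for two answer patterns in two secondary tables. As written, SAP 3.7.2 gives a non-pregnant cycle with Yes/blank or blank/No no exposure, and credits a blank cycle with the woman's Year 1 proportion.

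Under the assumptions above, the two-year denominator rises by 0.4% to 2.4% on correction, and with one pregnancy the index changes by less than 0.01 against an upper limit of about 1.9 to 2.3. With no pregnancies the index stays at 0 and only the upper limit moves. With no such records the effect is nil.

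The Year 1 primary result and the tables without estimation are numerically unchanged. This is a minor correction, worth making because the rule is incoherent and almost free to repair.

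**What to change.** Add one rule to SAP 3.7.2 for non-pregnant cycles with exactly one item answered:

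- If the known answer is intercourse No or backup Yes, count 0.
- Otherwise, include the cycle in the Step A count for 14.2.1-Y2M and 14.2.1-Y3M. In the tables without estimation, class it as missing; it adds 0 either way.
- Report the number of half-answered records by pattern.

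Because Step B is at or below the expected risk of these two patterns when answers are missing at random, the repaired rule still leans slightly conservative.

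The cost is one sentence, one programming condition and one count, with no new data. The downside is that backup-missing cycles would be estimated in Years 2 and 3 although Year 1 excludes them. The plan already accepts that for blank cycles, and the tables without estimation remain as the check.
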